Anxiety disorders are one of the most prevalent childhood mental health disorders^{5,6} with rates as high as 9% found in preschool children.⁷ Similar prevalence rates, symptom presentation and co-morbidity patterns are seen in preschool children as in the school-age period.⁸⁻¹¹ Anxiety disorders are debilitating disorders affecting all aspects of a child's life including their social development, academic achievement and family functioning.⁶ Most importantly, anxiety disorders are reliable predictors of long-term mental health difficulties.^{12,13} Childhood anxiety disorders rarely remit without treatment^{6,14,15} and even with remittance, high recurrence rates are evident.^{15,16} Low remittance rates are associated with an earlier age of onset, older age at intake, and more severe baseline symptoms.^{6,16} Burgeoning evidence suggests that treatment effects may be more robust in early childhood when there is increased neuroplasticity and room for larger developmental changes.^{10,17} This highlights the importance for early identification of anxiety disorders and development of effective treatments for young anxious children.

Social Anxiety Disorder (SAD) and Selective Mutism (SM)

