blinded to treatment condition and time of assessment, using the Clinician Global Assessment Scale [CGAS]⁶¹ in more children in the “*Taming Sneaky Fears for SAD and/or SM*” than children in the comparison group at post-intervention and at 6-month follow-up. A ≥10 point change means change from one category to the next on the CGAS.

A second objective of this study is to evaluate parent and teacher ratings of child symptomatology (SAD and SM) at home and in the classroom, respectively, over the course of the treatment program.

Hypothesis #4: Parents of children who attend the “*Taming Sneaky Fears for SAD and/or SM*” will report significantly fewer symptoms over the course of the study than those in the “Parent Psycho-education and Child Socialization” as measured by the parent Selective Mutism Questionnaire (SMQ)⁶² and the Social Anxiety Scale for Children Revised for Parents (SASC-P).⁶³ Similarly, teachers will report significantly fewer symptoms over the course of this study in children who attend the “*Taming Sneaky Fears for SAD and/or SM*” than those in the “Parent Psycho-education and Child Socialization,” as measured by the teacher School Speech Questionnaire (SSQ)⁶⁴ and the Social Anxiety Scale for Children Revised for Teachers (SASC-T).⁶³

A third objective is to explore factors within the child, parent and environment that predict treatment outcome (i.e., loss of at least one anxiety diagnosis post-treatment; this objective could not be explored in the original OMHF study due to the small sample size and lack of power). Factors hypothesized to predict treatment outcomes include within-the-child factors (age, gender, BI, and speech-language difficulties) and within-the-parent/environment factors (family history of SAD or SM, immigration status, and family stresses).

Hypothesis #5: The most significant factor to predict treatment outcome (i.e. lost diagnosis) at 6 months will be treatment group. The other factors (age, gender, BI, speech-language difficulties, family history of SAD or SM, immigrations status, family stresses) will not be significant in predicting treatment outcome.

METHODS:

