Recruitment: Children referred for an assessment of SAD and/or SM at either site are assessed by 1 of the 4 child psychiatrists, who obtains information about presenting problem, its impact on the child's functioning at school, home and with peers, and developmental, medical and family history. Eligible, interested children and families meet with a Clinical Research Project Coordinator (coordinator) who describes the study immediately post-assessment at either HSC or TEGH (depending on site where child was assessed). The coordinator obtains informed consent from parent(s) and assent from child, gives pre-treatment questionnaires to the parent(s), and schedules the first research assessment visit (Time 1) at HSC within 2 to 3 weeks of assessment and start of treatment group. Children and families not eligible for the study or who decline to participate are treated or referred for appropriate treatment as usually done in each clinic.

Measures: A demographic questionnaire (child's age and gender, parent's name, family composition, family history of SAD or SM, and immigration status) is completed by the parent at the start of the study.

A. Clinician Rated Measures:

- 1) The Anxiety Disorders Interview Schedule for DSM-IV, Parent Version (ADIS-P)⁵⁹ is used to assess SAD and/or SM. The ADIS-P has good reliability,⁶⁶ is sensitive to treatment effects in child anxiety studies,^{66,67} and has been used in a number of studies on preschoolers^{45,46,48} and SM treatment.⁵⁸ Clinical Severity Rating (ADIS-CSR) uses a 0 to 8 scale to measure clinical severity of diagnosis; a CSR of ≥ 4 indicates clinically significant symptoms and presence of an anxiety disorder. A trained independent clinician blinded to treatment type and time of assessment completes the CSR.
- 2) The Children's Global Assessment Scale (CGAS)⁶¹ assesses adaptive functioning during the previous month for children aged 4-16 years. It has high inter-rater and test-retest reliability. A trained independent clinician blinded to treatment type and time of assessment completes the CGAS.

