Pre-treatment Research Assessment (Time 1 [T1]) takes place ~2 weeks prior to group-treatment start. Parent questionnaires are reviewed by a Clinical Research Project Coordinator (CRPC) to ensure completion. The CRPC administers the ADIS-P with the parent and then completes the '10 Steps to Talking' with the child in the presence of the parent (video-recorded). The only speech and language assessment completed as part of the study is conducted (and video-recorded) at this T1 visit. Upon completion of the T1 visit, the CRPC **randomly assigns** each eligible child and parent to either the (1) "*Taming Sneaky Fears for SAD and/or SM*" parent and child group CBT program or (2) the "*Parent Psycho-education and Child Socialization*" group program, and informs them of group assignment. The online software *Sealed Envelope*TM (<https://www.sealedenvelope.com/>) is used to randomize. This program is commonly used by hospital research studies because it uses computer-generated sequences to allocate participants to each group. Allocation of participants uses sealed, opaque envelopes and remains concealed until study completion. The CRPC and lead child group and parent group therapists ([name]) are not blinded, however, the clinicians completing the post-intervention (T2) and 6-month follow up (T3) assessments are blind to treatment type, previous ratings on all measures, and time of assessment.

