Implementation of Treatment Protocols: Both group treatment protocols run concurrently, but on different days. A total of 5 “*Taming Sneaky Fears*” and 5 “*Parent Psycho-education and Child Socialization*” groups need to run over the course of the 2-year study with 8 - 9 children per group (total of 40 - 45 children per treatment arm over study period). Groups run weekly for 1 hour for nearly 3 months (10 + 1 sessions) starting in September 2015, October 2015, November 2015, March 2016, and April 2016. As the final treatment groups for the study are completed by mid-July 2016, the final 6-month follow-up takes place in mid-January 2017, prior to the end of the study (see Time line of Study p. 10). Regardless of the treatment program, the first treatment visit is for parents only at which time parents are introduced to the therapists and other parents in the group and provided a copy of the “*Parent Manual*” relevant for each group (either the Parent Manual for “*Taming Sneaky Fears for SAD and SM*” or the one for “*Parent Psycho-education and Child Socialization*” that includes handouts provided as part of the “*Improving Parent-Child Relationship*” series of videotapes).

In both treatment protocols, parents and children attend weekly, 1-hour group sessions for 10 consecutive weeks at HSC. In order for the 2 treatments to be comparable, each child group follows the same format, i.e., starts with a ‘review of the week’, followed by a story then craft activity and ends with a snack. At the end of each session, a child therapist drops into the parent group to inform parents about strategies and activities taught to children that day (typically, a 30-second general summary). At the mid-point of both group treatments, a child therapist meets with parent(s) individually to discuss their child’s progress. Therefore, children in both treatments receive equal opportunities for interaction with therapists and socialization with peers with the only difference between groups being that children in the “*Taming Sneaky Fears for SAD and/or SM*” group receive CBT while the children in the comparison group do not. Similarly, both parent groups start with a review of homework, then new information is provided and finally, homework is assigned; with the main difference between groups being that in “*Taming Sneaky Fears for SAD and/or SM*” parents receive CBT.

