Post-group Research Assessment (T2) and Longer-term (6-month) Post-group Research Follow-up (T3): Each post-treatment research visit takes ~2½ hours to complete, is video-taped and is similar to the T1 visit except there is no speech and language assessment. To ensure an unbiased assessment and clinician rating of the ADIS (-P and -CSR) and CGAS, a psychiatrist or graduate (PhD) student trained in the ADIS and blinded to treatment group, previous ratings, and time of assessment, administers the ADIS-P to the parents. This assessor then conducts the “10 Steps to Talking” protocol with the child in the presence of the parent. Parents also complete the same questionnaires used at T1, with the addition of one new questionnaire (the SWAN Rating scale). Parents are provided with teacher questionnaires prior to the end of treatment and bring them back (completed by teachers) at T2, while teacher questionnaires are mailed out to parents a few weeks prior to the 6-month post-intervention (T3) assessment and parents bring the completed questionnaires at the T3 visit. Teacher questionnaires are completed by teachers who know the child well as close to the assessment time as possible (e.g. if a research assessment is in July, the teacher completes the questionnaire prior to the end of school year).

Children receive stickers and parents are reimbursed \$20.00 to compensate for expenses such as parking and/or other expenses incurred because of participation in the research assessments at each of the T1, T2, T3 assessments. The 3 research assessments are video-recorded and ≥5% of randomly assigned recordings are reviewed by all assessors (coordinators + assessors at T2 and T3) to establish inter-rater

reliability on ADIS-CSR and CGAS. We acknowledge the difficulty in following families after treatment and to encourage subject retention, 1 of the coordinators contacts families by phone 3 months post-treatment and the need for ongoing monitoring and follow-up to maintain gains made is emphasized to parents.

Statistical Analysis and Data Analyses Plan:

Data for demographic variables will be summarized using counts, percentages, measures of central tendency (average, median, mode) and measures of sample variation (standard deviation, range).

Parametric statistics (average, standard deviation) will be used for interval and ratio data.

[figure not shown]

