To address Hypothesis 1, we will use a two-sided Chi-Square test with continuity correction to compare the difference between the two 2 groups in the proportion of children who lost diagnoses post-treatment (T2) and 6 months post-treatment (T3).

To test Hypothesis 2, we will use a repeated measures regression model on the ADIS-CSR and compare the two 2 treatment groups from pre-treatment (T1) to 6-month post treatment (T3). An interaction term between time and group will be introduced in the model in order to explore possible differences at different time points between the two groups. The assumptions of the model will be verified using residual analysis and, if necessary, transformations will be used in order to obtain a valid model. This repeated measures regression model will be used for Hypotheses 3 and 4 to assess child global functioning using CGAS and parent and teacher reports of child symptoms on SMQ, SASC-P/T and SSQ.

To examine Hypothesis 5, a logistic regression analysis will be employed. This will allow for the examination of the strength of multiple predictors on the likelihood that a child will lose an anxiety disorder diagnosis 6 months post-intervention (T3). The predictor factors that will be included in this model include group intervention (“*Taming Sneaky Fears for SAD and/or SM*” or “Parent Psycho-education and Child Socialization”), within-the-child factors (child’s age, sex, BI, and speech-language difficulties), parent factors (family history of SAD or SM), and environmental factors (family stress, immigration status). All the significant factors will be put into the model and non-significant predictors will be excluded. The model will control for age and sex of the child.

ORIGINALITY AND SIGNIFICANCE/RELEVANCE: This is the first RCT to assess the efficacy of “*Taming Sneaky Fears for SAD and/or SM*”, a group CBT treatment approach to treat 4 to 7 year old children with SM and/or SAD, which are anxiety disorders affecting as many as 36,340 children under age 14 in Ontario. The present study addresses methodological shortcomings of previous studies and builds on OMHF-funded previous work while addressing a significant clinical problem for which little convincing evidence for treatment efficacy exists. The present study represents an innovative treatment method that is brief, CBT-based, and group-focused.

Timeline of the Study:

REFERENCES

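### The planned H1 test is valid, but neither H1 nor H5 uses the T1 ADIS-CSR already collected for H2; a modest gain is available if its rater and timing are fixed first

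*Combined protocol and SAP*

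**What the plan says.** **Primary analysis.** The Statistical Analysis and Data Analyses Plan states: "To address Hypothesis 1, we will use a two-sided Chi-Square test with continuity correction". The comparison is made at T2 and at T3, with no covariate. The Sample Size Calculation uses the same test.

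**Model for predictors of diagnosis loss (H5).** The third objective states: "Factors hypothesized to predict treatment outcomes include within-the-child factors (age, gender, BI, and speech-language difficulties". It adds family history, immigration status and family stresses. The analysis plan repeats these factors plus treatment group. Baseline severity is on neither list.

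**Where the T1 CSR is used.** The H2 model of the ADIS-CSR is to "compare the two 2 treatment groups from pre-treatment (T1) to 6-month post treatment (T3"), so the T1 value is planned data. Under Measures, the CSR runs from 0 to 8, and 4 or more marks presence of a disorder. The primary outcome is loss of diagnosis on the same interview.

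**Why severity may matter.** The Background states: "Low remittance rates are associated with an earlier age of onset, older age at intake, and more severe baseline symptoms".

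**Who rates it.** Measures states: "A trained independent clinician blinded to treatment type and time of assessment completes the CSR". The Pre-treatment Research Assessment section states: "The CRPC administers the ADIS-P with the parent". The same coordinator then randomises when the T1 visit is complete, and is described as not blinded. The section on the T2 and T3 assessments has recordings "reviewed by all assessors (coordinators + assessors at T2 and T3") to check agreement on the CSR.

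**The concern.** The Background names three correlates of low remission. Only age at intake has a counterpart on the H5 list. Severity, which the trial measures on the outcome's own scale, is absent from both analyses of diagnosis loss.

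Two things are at stake. With 35 children per arm and 3 to 4 expected control events (35 × 0.10 = 3.5), a chance difference in severity carries into the H1 estimate, and some precision from data in hand goes unused. Also, a baseline covariate is safe only if it is fixed before allocation is known. No section says who assigns the T1 CSR or that it is final before randomisation. That gap already affects H2, and it would affect H1 once the covariate is added.

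**Working it through.** **1. The plan's own figure.** Inputs from the Sample Size Calculation: 42% and 10% (d = 0.32, mean rate 0.26), two-sided 0.05, continuity correction.

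- Uncorrected: n' = [1.960 × √(2 × 0.26 × 0.74) + 0.8416 × √(0.42 × 0.58 + 0.10 × 0.90)]² / 0.32² = (1.2158 + 0.4861)² / 0.1024 = 28.3.
- Corrected: n = (n'/4) × [1 + √(1 + 4/(n'd))]² = 34.3, so 35 per arm.
- Inverting at n = 35 gives n' = 29.03 and z = (√29.03 × 0.32 − 1.2158)/0.5776 = 0.880, so power is 81.1%. The plan states 81%.
- Dropout: 70/0.80 = 87.5, so 88, as stated.

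**2. Exact behaviour of the planned test.** Binomial enumeration at 35 per arm gives power of 83.2%. Its size lies between 1.3% and just under 3% for common rates from 10% to 50%. Without the correction, power is 88.9%, so the correction alone costs 88.9 − 83.2 = 5.7 points.

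**3. The adjusted test.** Fit a logistic model of diagnosis loss on T1 CSR only. Let U be observed minus fitted losses summed over the CBT arm, and V its variance given that fit. The statistic is (|U| − 0.5)²/V, referred to 3.84. With the CSR left out, this is exactly the planned corrected chi-square, because |ad − bc| = N|U|. The comparison below therefore isolates the covariate.

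**4. Power.** The documents give no CSR distribution and no CSR-outcome association. Assumed: T1 CSR 4 to 8 with probabilities 0.15/0.25/0.30/0.20/0.10 (SD 1.19), an odds ratio (OR) for less severe baseline of 1.0 to 2.7 per SD, independent children, and marginal rates held at 42% and 10%. There were 10,000 simulated trials per setting (Monte Carlo SE about 0.4 points).

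| OR per SD | Planned | Adjusted, corrected | Difference |
|---|---|---|---|
| 1.0 | 83.3% | 82.4% | −0.9 |
| 1.5 | 82.7% | 83.7% | +1.0 |
| 2.0 | 83.7% | 85.4% | +1.7 |
| 2.7 | 83.3% | 87.1% | +3.8 |

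A separate set of simulated trials gave 81.6/82.8/83.8/82.8% planned and 81.3/83.0/85.5/88.0% adjusted, differences of −0.3, +0.2, +1.7 and +5.2. The size of the adjusted test was about 1% to 3%.

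**5. Precision and imbalance.** The SD of the risk difference falls by 1.2%, 3.7% and 5.9% at OR 1.5, 2.0 and 2.7. The SE of the standardised T1 imbalance is √(2/35) = 0.239, so an imbalance of 0.3 SD or more has probability 21%. At 0.3 SD, the simulated slopes move the unadjusted difference by 0.3 × 0.068 = 2.0, 0.3 × 0.110 = 3.3 and 0.3 × 0.134 = 4.0 points at those ORs. The adjusted difference moves by 0.2 or less. The SE of the unadjusted difference is √[(0.42 × 0.58 + 0.10 × 0.90)/35] = 9.8 points.

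**6. Rater and timing.** Measures assigns the CSR to a blinded independent clinician. The T1 section has the coordinator give the interview and then randomise. The T2/T3 section counts coordinators among the assessors. These fit together if the coordinator rates T1 before allocation, but the text does not say so. Purely as an illustration: if 25% or 50% of CBT children were recorded one CSR point higher after allocation, the adjusted difference would rise by 1.8 or 3.6 points at OR 2.0. The unadjusted difference would not move.

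**The case against.** The strongest objection is that this is a refinement of a sound primary analysis. The planned test holds its level and matches the sample size. The gain rests wholly on an assumed OR and CSR distribution. The Background statement concerns childhood anxiety in general, does not name the CSR and gives no strength. Children enter already diagnosed, so the CSR may occupy a narrow range. All of this stands, and it limits the size of the point.

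Chance imbalance is indeed already covered by the unadjusted standard error: 2 to 4 points against 9.8. Adjustment makes the result less sensitive to imbalance; it does not remove a bias.

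Two practical objections also stand and are met in the fix. First, SAD and SM often coexist, by the protocol's own account, so a child may have two CSRs and the covariate must be defined. Second, the plan reports that no comparison child lost the diagnosis in the previous study. Zero events among 35 controls has probability 0.90³⁵ = 2.5% at a true 10% rate, 0.95³⁵ = 17% at 5% and 0.98³⁵ = 49% at 2%. The score test survives this, because its fitted model has no arm term, but a model-based interval does not.

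A reader might infer that the T1 CSR is scored by an unblinded rater who knows the allocation. The documents do not support that. Randomisation follows completion of the T1 visit, so rating before allocation is the natural reading. What is missing is the statement.

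**Conclusion.** The omission is plain in the text: neither H1 nor H5 uses a baseline score that is collected anyway, lies on the outcome's own instrument and has some prognostic support in the Background. The planned test remains valid for independent children at one time point.

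The expected effect of adjustment is about −1 to +5 points of power: close to zero at OR 1.0 to 1.5 per SD and 2 to 5 points at 2.0 to 2.7. The SD of the risk difference falls by 1% to 6%, and chance severity imbalance has less influence. The ORs and the CSR distribution are assumptions. Different raters at T1 and at T2/T3 could shrink the gain.

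A reader might infer that the unadjusted test is biased or the trial underpowered, or that adjustment lifts power to about 90%. The figures support none of these. The stated 81% reproduces, and most of any rise towards 90% comes from dropping the continuity correction.

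The change is worth making because it is cheap and must be specified in advance. The rater statement is the firmer part, since H2 needs it regardless. Shared therapy groups, the ordering of T2 and T3, and the counting of children below CSR 4 at T1 are separate matters and not part of this conclusion.

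**What to change.** 1. Pre-specify one H1 analysis adjusted for the T1 CSR: the score test for arm given T1 CSR, keeping the 0.5 continuity correction.
2. Report a standardised risk difference with a 95% CI on the same independence basis as the test. State that the test decides significance, because the interval carries no continuity correction and can occasionally exclude zero when the test does not reject.
3. Keep the planned corrected chi-square alongside it, and name in advance which of the two decides H1, so that they do not become two chances.
4. Define the CSR for a child with both SAD and SM, for example that of the primary diagnosis, or the higher if they are co-primary.
5. Name a fallback interval if an arm has no events, such as an unadjusted score interval for the risk difference.
6. State who scores the T1 CSR and that it is locked before allocation. Reconcile Measures, the T1 assessment section and the T2/T3 assessment section. If a locked pre-allocation rating cannot be shown, the planned test stays as the only H1 analysis.

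H5 is not the place to make the correction, because its rule of excluding non-significant predictors could remove the CSR again.

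**Cost.** Analysis-plan wording and one locking step before randomisation. No new data are needed and no child is excluded. The downside is up to about 1 point of power if the CSR is not prognostic.

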RESEARCH QUESTIONS AND HYPOTHESES TO BE TESTED: This study builds on our previous OMHF funded work in which we demonstrated that 5 to 7 year old children with anxiety disorders randomized to the “*Taming Sneaky Fears*” group CBT program exhibited greater improvements in global functioning and lost more diagnoses than those randomized to the parent only group CBT program. Starting with a previously proven treatment protocol that is engaging and teaches young children various CBT strategies, we use a slightly revised and refined treatment protocol specifically for children with SAD and/or SM and their parents and expand the age range down to 4 years. The primary objective of this study is to assess the efficacy of the brief (10 concurrent parent and child + 1 parent only), refined, group CBT program “*Taming Sneaky Fears for SAD and/or SM*” in the treatment of 4 to 7 year old children with SAD and/or SM.

Hypothesis #1: The “*Taming Sneaky Fears for SAD and/or SM*” group CBT treatment is more efficacious than a comparison intervention, “Parent Psycho-education and Child Socialization” such that more children in the “*Taming Sneaky Fears for SAD and SM*” group CBT will lose their primary diagnosis of SAD and/or SM, compared to children in the comparison group. Our primary outcome measure will be loss of diagnosis of SAD and/or SM as assessed by an independent clinician blinded to treatment condition and time of assessment using a semi-structured interview, the Anxiety Disorders Interview Schedule for Parents [ADIS-P]),⁵⁹ post-intervention and at 6-month follow-up.

Hypothesis #2: In those children who do not lose their primary diagnosis of SAD and/or SM, there will be a 2.0 or greater point improvement in anxiety severity (measured by an independent assessor blinded to treatment condition and time of assessment, using the ADIS-P Clinical Severity Rating [ADIS-CSR]) in more children in the “*Taming Sneaky Fears for SAD and/or SM*” program than children in the comparison group at post-intervention and at 6-month follow-up. This hypothesis is based upon a recent meta-analysis that suggests a 2.0 change in the ADIS-CSR is a clinical meaningful change.⁶¹

Hypothesis #3: In those children who do not lose their primary diagnosis of SAD and/or SM, there will be a 10.0 or greater point improvement in global functioning (measured by an independent assessor

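### The repeated measures model for Hypotheses 2 to 4 should adjust for the pre-randomisation T1 score, or constrain arm means to be equal at T1, and should name the T2 and T3 arm differences as its tests

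*Combined protocol and SAP*

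**What the plan says.** Under Statistical Analysis and Data Analyses Plan, Hypothesis 2 is tested with a repeated measures regression on the ADIS-CSR that will "compare the two 2 treatment groups from pre-treatment (T1) to 6-month post treatment (T3"). The plan adds: "An interaction term between time and group will be introduced in the model in order to explore possible differences at different time points". It then extends the method to the CGAS, SMQ, SASC-P/T and SSQ: "This repeated measures regression model will be used for Hypotheses 3 and 4". It does not say which coefficient or contrast decides each hypothesis. It also gives no baseline covariate, no constraint on the T1 means and no covariance structure.

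The section on the Pre-treatment Research Assessment places randomisation after the T1 visit is complete. On who performs T1, it says "The CRPC administers the ADIS-P with the parent". The clinician-rated measures section says "A trained independent clinician blinded to treatment type and time of assessment completes the CSR" and assigns the CGAS in the same way. The section on the T2 and T3 assessments has a blinded psychiatrist or doctoral student administer the interview at those visits. It lists coordinators among the assessors whose CSR and CGAS reliability is checked on at least 5% of recordings.

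Hypotheses 2 and 3 are worded as responder comparisons among children who keep the diagnosis: "there will be a 2.0 or greater point improvement in anxiety severity" and "there will be a 10.0 or greater point improvement in global functioning", each at T2 and T3.

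**The concern.** T1 is measured before allocation, so the expected difference between arms at T1 is zero and any treatment effect lies at T2 and T3. A model that gives each arm its own free T1 mean does not use that fact. Its group-by-time term is then a difference in change from T1, which carries all of the T1 noise into the comparison. Adjusting for T1, or forcing the arms to share a T1 mean, removes part of that noise with the same data.

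The wording also leaves the deciding test open. The term that carries the treatment effect is described as exploratory and no other term is named. If software output is read with T1 as the reference time, the coefficient labelled group is the T1 difference, which has expectation zero. If a group effect averaged over all three visits is reported, a visit with no possible effect is mixed in.

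At stake is power on every Hypothesis 2 to 4 scale. None of these has its own power calculation, and about 70 completers are planned.

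**Working it through.** **Plan's own figure (Hypothesis 1 only).** Inputs from Sample Size Calculation: 42% against 10%, two-sided 5%, power 81%, continuity correction.
- Uncorrected: n' = [1.96√(2×0.26×0.74) + 0.878√(0.42×0.58 + 0.10×0.90)]² / 0.32² = (1.216 + 0.507)² / 0.1024 ≈ 29 per arm.
- Corrected: n = (n'/4)[1 + √(1 + 4/(0.32n'))]² ≈ 35 per arm, 70 in all. Power is 80.4% at 69 and 81.1% at 70.
- Dropout: 70/0.80 = 87.5, so 88.

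These figures reproduce, and nothing below alters them. The plan states no power for Hypotheses 2 to 4.

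**Inputs for the check.** From the documents: n = 35 per arm, three visits, randomisation after T1, two-sided 5% (stated for Hypothesis 1 and carried over). Assumed: effect d = 0.5 SD at both T2 and T3, equal SDs at all visits, and one common correlation r of 0.3, 0.5 or 0.7.

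Power = Φ(effect/√(2v/n) − 1.96), where v is the per-child variance in SD² units.

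**One visit.** Change from T1: v = 2(1−r). Adjusted for T1: v = 1−r². The ratio is (1−r²)/[2(1−r)] = (1+r)/2, that is 0.65, 0.75 and 0.85, or variance 35, 25 and 15% lower. Example at r = 0.5:
- Adjusted: 0.5/√(2×0.75/35) = 2.415; less 1.96 = 0.455; power 68%.
- Change: 0.5/√(2×1.0/35) = 2.092; less 1.96 = 0.132; power 55%.

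**Mean of T2 and T3.** Change: v = (1+r)/2 + 1 − 2r = 1.05, 0.75, 0.45. Adjusted: v = (1+r)/2 − r² = 0.56, 0.50, 0.36. The ratios are 0.53, 0.67 and 0.80.

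**Group effect averaged over T1 to T3.** The effect is (0 + d + d)/3 = 2d/3, and v = (1+2r)/3 = 0.533, 0.667, 0.800.

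| Power at d = 0.5 SD | r = 0.3 | r = 0.5 | r = 0.7 |
|---|---|---|---|
| One visit, change from T1 | 42% | 55% | 77% |
| One visit, adjusted for T1 | 59% | 68% | 83% |
| Mean of T2 and T3, change | 53% | 68% | 88% |
| Mean of T2 and T3, adjusted | 80% | 84% | 94% |
| Group effect averaged over T1 to T3 | 48% | 40% | 34% |

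At r below 0.5, change is noisier than ignoring T1 altogether, because 2(1−r) exceeds 1. At r = 0.3 the T3 score alone gives 55%, against 42% for change.

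**Sensitivity to the effect.** At 0.67 SD, single-visit power is 66, 80, 95% for change and 84, 90, 98% adjusted. At 0.8 SD it is 81, 92, 99% and 94, 97, above 99%. The ordering holds, but the gap narrows.

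**Simulation** (20,000 runs, d = 0.67, r = 0.5). The averaged group effect was 0.447, which is two thirds of 0.67, with power 61% (formula 63%). The change and adjusted contrasts on the T2–T3 mean both recovered 0.670, with power 89% and 97% (formula 90% and 98%).

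**The case against.** The strongest reply is that the plan does not commit to a poor test. The interaction sits inside the model used to test Hypothesis 2, and comparing arms from T1 to T3 can naturally mean comparing change, which is undiluted and unbiased. That stands. A reader might infer that the plan shrinks the effect by a third. The documents do not support this as a statement of fact: it happens only if the averaged group effect is taken as the test, and the plan does not say so. The wording merely leaves that reading open.

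A reader might also infer that having T1 among the outcomes is an error that throws the baseline away. It is not. The interaction uses T1 through change, and a model with T1 as an outcome and equal arm means at T1 is about as efficient as covariate adjustment. The loss is partial efficiency.

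It is also tempting to set the 34 to 48% of the averaged effect against the 80 to 94% of the adjusted T2–T3 mean. That overstates the gain from tests made visit by visit. Like for like at one visit, the gain is 17, 12 and 6 points before rounding.

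On raters, a reader might conclude that the coordinator scores the T1 ADIS-CSR and CGAS. The text says only that the coordinator administers the T1 interview, while the measures section assigns both ratings to a blinded independent clinician. Counting coordinators among the assessors for reliability suggests that they may rate, but does not establish it. A rater shift common to both arms would in any case cancel in the between-arm comparison.

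Finally, adjustment may not be possible everywhere. Teacher questionnaires are described only for T2 and T3, so a T1 SSQ or SASC-T score cannot be presumed. This objection stands and limits the fix.

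**Conclusion.** The point holds as one of efficiency and of an unnamed test on secondary hypotheses. It is not a point about bias, and it does not touch Hypothesis 1 or its sample size. Where change from T1 is the test, baseline adjustment lowers the single-visit variance by 35, 25 or 15% at r = 0.3, 0.5 or 0.7. For the T2–T3 mean the reduction is 47, 33 or 20%. The variance ratio is algebra under equal variances. The power figures also rest on an assumed effect, a common correlation and 35 analysed children per arm, and the documents give no SD, correlation or mean effect for these scales. The loss to two thirds of the effect is conditional on a reading that the plan permits but does not state.

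Two limits remain. The account of who rates the T1 ADIS-CSR and CGAS is inconsistent across sections and needs reconciling. In addition, a mean-score model, adjusted or not, does not by itself test the responder shares among children keeping the diagnosis that Hypotheses 2 and 3 state. At the planning rates, about 20 (0.58×35) and 32 (0.90×35) children per arm would form that subset at T2, not 35.

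**What to change.** For each Hypothesis 2 to 4 scale with a T1 score, specify one of two models:
- T2 and T3 as outcomes, with the child's T1 score as covariate; or
- T1, T2 and T3 as outcomes, with arm means constrained equal at T1. This also keeps children who lack a T1 score, whom a plain covariate model would drop.

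State the arm differences at T2 and at T3 as the tests, and state the covariance structure. Apply this to the SSQ and SASC-T only if a T1 teacher score is collected, and say in the plan whether it is.

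Separately, reconcile the clinician-rated measures, T1 and T2/T3 sections on who rates the T1 ADIS-CSR and CGAS. If the T1 rater differs from the later raters, rest conclusions on between-arm differences and not on within-arm change. Say also how the responder shares in Hypotheses 2 and 3 will be analysed, since this change does not supply that.

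The cost is SAP wording. Where T1 scores exist, the data are the same.
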